Repeated measures analysis has the advantage of increased power compared to group allocations and reduction in error variance associated with individual difference, as each subject acts as its own control. This is important for studying amputees as the group is a small proportion of the total population, and with specific inclusion/exclusion criteria the total eligible population becomes very small, making it difficult to find and recruit subjects to attain an acceptable level of power. This limited population pool often results in a slightly heterogeneous sample, as the amputees available are few and far between, in every sense. Furthermore, no single amputation procedure and therefore amputated stump is exactly the same, making the experience of each amputee unique. The within-subject design significantly reduces the individual differences when comparing the two conditions.

Several studies have provided evidence for the clinical performance of previous versions of the Rheo Knee, which is equivalent to the investigational device and has the same function and intended use, those are detailed in the Literature review device report [1]. The current study is due to a design iteration after modifications to the device from the previous study CIP2022022514 [9].

[figure not shown]
For full details of existing clinical data and pre-clinical data on the investigational device see Investigators Brochure [2].

7 Objectives and Hypotheses

In this trial, the primary objective is to evaluate the efficacy of the investigational device compared to the former Version Rheo Knee (XC) and in addition (mandatory) to other passive MPKs (e.g. C-leg 4, Genium, X3, Plié 3, Orion 3, Quattro, Allux) regarding performance improvements and satisfaction in descending activities for moderate to high active prosthesis users within the intended population for the investigational device.

Additionally, the overall satisfaction for activities of daily living will be evaluated after a certain time of use (4 weeks home use).

The following clinical claims/MNBA items as defined in the Clinical evaluation plan [3] are to be evaluated:

The hypothesis and endpoints are specified in Table 4 and Table 5.

For all hypothesis:

[figure not shown]
μ_1 is average of measurements at baseline (comparator);

[figure not shown]
μ_2 is the average of measurements at 4 week follow up (investigational device);

Table 5 - Endpoints, test methods and hypotheses

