	Hypothesis	Construct & Test Methods	Endpoints	Acceptance Criteria
A	Navii shows better or no worse results in Ramp, Stairs and Level Ground activities compared to prescribed prosthesis	Specific questions (see Annex 8.8)	Rating: Same, better, worse	Overall results for Navii are same or better than for Rheo Knee, with no more than 20% rating it worse, overall for all questions.
B	Navii shows a good level of overall satisfaction in activities of daily living	Subset of PEQ (see Annex 8.4) Specific Questions (see Annex 8.8)	PEQ Rating	Comparison Subset PEQ pre vs post. Navii not worse than prescribed.
C	Mobility is no worse with Navii compared to prescribed MPK	2 MWT	Distance walked in 2MWT (meters)	No significant reduction in distance walked on 2MWT with prescribed knee/Navii
D	Balance during ambulation is no worse with Navii compared to prescribed MPK	TUG	Time to complete TUG (seconds)	No significant increase in time needed to complete TUG with prescribed knee/Navii
E	Mobility is no worse with Navii compared to prescribed MPK	PlusM	PlusM Score	No significant reduction in PlusM Score with prescribed knee/Navii
F	Gather experiences on perceived safety and balance with Navii compared to prescribed knee.	ABC	ABC Score (0-100%)	Acceptable patient-reported perceived safety and performance

7.1 Additional Outcome measures:

8 Design of the Clinical Investigation

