8.1 General

The test will be a non-randomized single group repeated measures open label prospective design with observational and self-report measures.

Amputees are a small proportion of the general population. The population group specified in the inclusion/exclusion criteria is a further subsample of amputees. For practical reasons, i.e. to achieve statistical power, it is therefore more feasible to use within-subject comparison rather than creating study arms to compare. Furthermore, as mobile amputees generally have and use a prosthetic device for their daily activities, within-comparison is feasible comparing to the subject's previous device.

All investigational activities will be conducted at the Össur Orlando site.

As stated above the primary endpoint is Satisfaction on descending stairs, see Table 5, and the secondary endpoints are satisfaction on descending ramps, balance confidence and standing comfort in that respective order of significance. In addition, there are two exploratory endpoints on mobility and balance during ambulation. See previous chapter on objectives and hypothesis and Table 5 for rationale.

Drop-outs and withdrawals will not be replaced.

Instruments for data collection will include the following:

The Prosthesis Evaluation Questionnaire (PEQ) measures prosthetic-related quality of life. It consists of 82 items grouped into nine subscales. In addition, there are individual questions not contained in the subscales regarding satisfaction, pain, transfers, prosthetic care, self-efficacy, and importance¹⁸. This study will include a set of subscales from the PEQ, including specific questions on descending activities.

TUG The Timed Up and Go (TUG) is a tool used to test basic mobility skills by asking the subject to stand up from a chair (which should not be leaned up against a wall), walk a distance of 3 meters, turn around, walk back to the chair and sit down

2MWT is a measurement of endurance that assesses walking distance over two minutes.

ABC is a Patient-reported outcome measure that asks individuals to rate how confident they are that they will not lose their balance while performing 16 different activities.

PLUS-M (Prosthetic Limb Users Survey of Mobility) is a self-report instrument for measuring mobility of adults with lower limb amputation.

Specific questionnaire: In-house generated questionnaire on specific features in the investigational device.

Log file: User should log device use and events.

Video

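### Section 8.1's primary endpoint, satisfaction on descending stairs, has no row of its own in Table 5, and row A's 20% limit as worded cannot decide it

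*Combined protocol and SAP*

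**What the plan says.** Section 8.1 states that "the primary endpoint is Satisfaction on descending stairs, see Table 5", and that "the secondary endpoints are satisfaction on descending ramps, balance confidence and standing comfort in that respective order of significance".

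Table 5 in section 7 has six visible rows, none marked primary:

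- **Row A.** Hypothesis: "Navii shows better or no worse results in Ramp, Stairs and Level Ground activities compared to prescribed prosthesis". The endpoint is a three-way rating (same, better, worse) from the specific questions in Annex 8.8. Criterion: "Overall results for Navii are same or better than for Rheo Knee, with no more than 20% rating it worse, overall for all questions".
- **Row B.** Overall satisfaction in daily living, from a PEQ subset and specific questions. Criterion: "Comparison Subset PEQ pre vs post. Navii not worse than prescribed".
- **Rows C to F.** 2MWT, TUG, PLUS-M and ABC.

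Section 10.1 assesses the primary hypothesis by descriptive statistics only. It gives mixed models to B, C, D and E, and exploratory methods to F. Section 7 says that "The hypothesis and endpoints are specified in Table 4 and Table 5", and sections 10.1 and 10.2 send the reader to Table 4 for acceptance and pass/fail criteria.

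On the comparator, the section 7 objective is a comparison with the former Rheo Knee (XC) and "in addition (mandatory) to other passive MPKs". Section 8.2 accepts either kind of knee. Up to 13 subjects are enrolled (section 8.2), and at least 10 must finish (section 8.3).

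**The concern.** The endpoint called primary in section 8.1 and the hypothesis treated as primary in section 10.1 are different things. One is satisfaction with a single activity. The other is a composite over three activities whose wording mentions neither descent nor satisfaction. Row B mentions satisfaction but not stairs, and its criterion has no numeric limit.

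Row A's limit is the only numeric one in the table, and it is open in two respects. It can be read as a share of subjects or as a share of answers pooled over the questions. It is also set against Rheo Knee, although some subjects may be users of another passive MPK.

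Section 6 says the study is meant primarily to confirm the pilot's indications on descending activities. With 10 to 13 unblinded subjects and a descriptive analysis, the protection against a favourable reading chosen afterwards is a primary endpoint and limit fixed in advance. The visible text does not supply that.

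**Working it through.** The plan gives no derivation of the 20% limit, so there is no figure to reproduce. The check asks what the limit allows on stair descent.

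**Inputs.** From the documents: a limit of 20% (Table 5, row A) and n = 10 to 13 (sections 8.2 and 8.3). Assumed, because Annex 8.8 is redacted: q specific questions, exactly one of them on stair descent, and every subject answering all of them.

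**Step 1: which row is primary.** Section 10.1 assigns methods by letter to B, C, D, E and F and handles the primary hypothesis separately. Only A remains. Nothing in Table 5 says so, and row A is not the endpoint named in section 8.1.

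**Step 2: limit counted over answers.** Largest permitted number of worse answers = floor(0.20 × n × q).

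| q | n = 10 | n = 13 |
|---|---|---|
| 3 | floor(6.0) = 6 | floor(7.8) = 7 |
| 4 | floor(8.0) = 8 | floor(10.4) = 10 |
| 5 | floor(10.0) = 10 | floor(13.0) = 13 |

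If every worse answer falls on the stair item, the 20% clause is met with stair descent worse in 6/10 or 7/13 subjects at q = 3, in 8/10 or 10/13 at q = 4, and in all subjects at q = 5. For larger q the pooled share with all subjects worse on stairs is 1/q, which is below 20%.

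These are the most lenient cases. With a bare majority worse on stairs (6/10 or 7/13), the worse answers still allowed elsewhere are the limit minus 6 or 7:

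- q = 3: 0 of 20 or 0 of 26
- q = 4: 2 of 30 or 3 of 39
- q = 5: 4 of 40 or 6 of 52

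**Step 3: limit counted over subjects, by overall verdict.** Suppose a subject counts as rating Navii worse when most of that subject's answers are worse (an assumption; the plan has no rule). With q = 5 and every subject worse on stairs only, each has 1 worse answer of 5. No subject then counts as worse, and 0/10 meets the limit. Choosing subjects as the unit does not protect the stair endpoint.

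**Step 4: the unit still matters.** Take n = 10, q = 10, and four subjects who each give 5 worse answers. Over answers this is 20/100 = 20%, which meets the limit. Over subjects it is 4/10 = 40%, which fails if a subject with half the items worse is counted as rating it worse.

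**Step 5: missing ratings.** Drop-outs are not replaced (section 8.1). If 13 are fitted, 10 have a 4-week rating and 2 of those are worse, then 2/10 = 20% meets the limit. Counting the 3 without a rating as worse gives 5/13 = 38%, which does not.

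**The case against.** The strongest reply is that text is missing. Annex 8.8 is redacted, Table 4 is cited but not visible, the list of claims in section 7 is empty, and section 7.1 is a bare heading. Endpoint definitions could sit in any of these. This stands as a limit on the point but does not remove it. Section 8.1 sends the reader to Table 5, which is visible, and sections 10.1 and 10.2 give Table 4 the title that section 7 prints on Table 5, so a numbering slip is plausible. If a separate Table 4 does define the endpoint, section 8.1 cites the wrong table.

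A reader might infer more than the documents support:

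- **That stair descent is not measured.** Row A names stairs, and section 8.1 says "This study will include a set of subscales from the PEQ, including specific questions on descending activities". An item may well exist. What is missing is a row and a limit for it.
- **That stating the unit settles the matter.** A limit counted by subject on the stair item alone would stop a majority-worse result from passing. Row A, however, applies its limit over all questions together, so that would be a new criterion and not a second reading of row A.
- **That section 8.1's secondary ranking is contradicted throughout.** Standing comfort has no visible row but may be in the missing text. Exploratory methods for row F describe an analysis, not necessarily an endpoint's rank.
- **That section 10.1's comparison of prior and post rates cannot fit a same/better/worse rating.** Section 8.4 has the device-specific questionnaires filled in at two time points, so the rating could be derived from paired answers. The form is redacted.

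It is also fair to say that the analysis is descriptive in a convenience sample. Section 10.2 nevertheless refers to pass/fail criteria, so a decision will be read from the table.

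**Conclusion.** The point holds on the visible text and should be corrected before data are seen. Sections 8.1 and 10.1 and Table 5 do not agree on one primary endpoint. Row A's limit lacks a unit, and its comparator disagrees with its own hypothesis. Because the limit is taken over all questions, it cannot decide stair descent: pooled over answers, a majority worse on stairs is compatible with the 20% clause at q = 3, and every subject worse at q = 5 or more.

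Those figures assume a single stair-descent item, complete answers and no worse answers elsewhere. They show what the clause permits, not what is likely. They concern the 20% clause only; row A also asks that overall results be the same or better, without defining that.

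**What to change.** Before data are seen:

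1. Make section 8.1, Table 5 (and Table 4, if it exists) and section 10.1 name the same primary endpoint. Either give stair descent its own row, with one named item, the 4-week visit and its own stated limit on worse ratings, after confirming that such an item exists; or correct section 8.1 to say that row A as a whole is primary.
2. State whether row A's 20% counts subjects or answers. Report the stair-descent and ramp-descent items separately whichever is chosen.
3. Set row A's criterion against the prescribed prosthesis, as its hypothesis does. Describe Rheo Knee users and other-MPK users separately, since section 7 asks for both comparisons. Reconcile this with section 10.1, which rules out subgroup analysis while also mentioning exploratory subgroup work.
4. State how fitted subjects without a 4-week rating count, and show the result with them counted as worse as a sensitivity check.
5. Say in section 10.1 how the same/better/worse rating is obtained and summarised: proportions, with an exact interval as description only. For 2/13 the 95% Clopper-Pearson interval is 1.9% to 45.4%.

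**Cost.** Section 11.1 reserves simple notification for changes unrelated to objectives or endpoints, so this is an amendment that the IRB must evaluate. If the 20% limit is moved to the stair item, the criterion becomes harder: floor(0.2 × 10) = floor(0.2 × 13) = 2 worse ratings allowed. With a true worse rate of 10%, the chance of 3 or more is 1 − (0.349 + 0.387 + 0.194) = 7% at n = 10 and 1 − (0.254 + 0.367 + 0.245) = 13% at n = 13.

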Hydraulic MPKs consist of an integrated microprocessor-controlled linear hydraulic system in combination with a control algorithm. They generate knee joint resistances hydraulically with microprocessor-controlled, motorized valves. This enables continuous variations in the hydraulic resistance to be set for both movement directions. The magnetorheological fluid creates shear forces in comparison to an increase of pressure in a hydraulic system. The increased system pressure can lead to higher temperatures and risk of leakage.

The previous version of the investigational device (RK III/RK XC) features the same intended use, same clinical purpose, same user population, same placement below the socket, uses a battery powered system and is controlled through a software application that can be user configured through a separate computer interface/mobile device. The investigational device is an enhancement of the previous version, functional features and indication are equivalent to previous version and the same critical functions apply. Features that have been added include a mechanical stance locking feature that allows the user to manually lock the knee in 3 different positions in stance and the device will be waterproof. The investigational device also includes functions that were only included in the Rheo Knee XC configuration of the previous version; automatic cycling and running detection and a stair ascent mode.

Results of a pilot stage exploratory clinical investigation including 25 subjects indicate that the investigational device had similar or better performance compared to previous versions of the Rheo knee regarding satisfaction on descending activities. This investigation is designed primarily to confirm these indications and that the performance of the investigational device regarding descending activities is comparable/no worse than Rheo Knee or hydraulic MPKs.

Study Design

[figure not shown]

Figure 2 - Study design and instruments

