The **LPI** can withdraw the participant from the trial at any time. The reasons shall be documented. There are no pre-specified criteria for discontinuation of participants from the trial. The discontinuation of participants in the trial will not result in replacement with new participants. If withdrawal is due to problems related to the investigational device the participant will be asked for permission to follow the status/condition outside the clinical investigation. The follow-up will be individualized.

Screening will be supported by Össur customers (prosthetic clinics) with potential for users fitting into the inclusion criteria.

Enrollment will take place at the Össur site in Orlando.

The total time period required to implement the clinical investigation is expected to be 12 weeks. Each individual subject is expected to participate in the clinical investigation for 4 weeks. The estimated time needed to include this number (enrolment period) is 6 weeks.

At least 10 subjects are required to finish the protocol for statistical data analysis, as specified in chapter **10.2 Sample size calculation**.

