10.1 Statistical design and procedures

The primary hypothesis will be assessed with descriptive statistics only, comparing the rates prior-evaluation (current device) and post-evaluation (investigational device). For hypotheses B, C, D, E will be assessed with mixed models effects where MPK type is used as fixed effect, subgroup analysis, and subject as random effect. F will be assessed with exploratory methods. All data will be analyzed exploratively for subgroup effects for input into further studies but not used to support claims.

Acceptance criteria for the data, as applicable, is defined in Table 4 **Endpoints, test methods and hypotheses**. Subgroup analysis will not be performed as no subgroups are defined.

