10.2 Sample size calculation

A convenience sample of up to 13 subjects are expected to complete the procedures.

For pass/fail criteria, see Table 4 **Endpoints, test methods and hypotheses**.

11 Amendments and Deviations from the Protocol (CIP)

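### The primary 20% rule accepts 'no worse' on a bare observed proportion, which 10 to 13 subjects cannot support if each gives one overall rating

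*Combined protocol and SAP*

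**What the plan says.** Section 6 reports a 25-subject exploratory pilot and then states the purpose of this trial: "This investigation is designed primarily to confirm these indications", and to show that performance in descending activities is at least not worse than with Rheo Knee or hydraulic microprocessor knees.

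In section 7, Table 5 row A turns this into a criterion. The endpoint is "Rating: Same, better, worse". Acceptance requires overall results that are the same or better, "with no more than 20% rating it worse, overall for all questions".

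Section 10.1 says: "The primary hypothesis will be assessed with descriptive statistics only". It assigns other methods to hypotheses B to F, so this sentence must refer to A. It gives no interval, test or error rate for A. Section 10.2 calls the criteria pass/fail.

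On numbers, section 10.2 says "A convenience sample of up to 13 subjects are expected to complete the procedures". Section 8.3 says "At least 10 subjects are required to finish the protocol for statistical data analysis" and cites section 10.2 for this. Section 8.1 adds: "Drop-outs and withdrawals will not be replaced".

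**The concern.** A purely descriptive aim needs no threshold. Here an observed proportion is set against 20%, the outcome is labelled acceptance, and the stated purpose is confirmation. With 10 to 13 subjects, an observed share of 20% or less is compatible with a much larger true share. Nothing in the visible text tells a reader of the result how uncertain a pass is. What is at stake is the main conclusion: 'no worse' could be accepted on data that do not rule out a substantially worse reception.

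**Working it through.** **Plan's own figure.** There is none to reproduce. Section 10.2 gives a convenience sample without alpha, power, expected rate or formula.

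**Inputs from the plan.** Threshold 20% (Table 5 row A); n from 10 (section 8.3) to 13 (section 10.2).

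**Assumptions.** One overall rating per subject, subjects independent, and exact (Clopper-Pearson) limits at 95%, with a two-sided limit using 0.025 in the upper tail and a one-sided limit using 0.05.

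**Step 1: how many 'worse' may pass.** 0.20 × n is 2.0, 2.2, 2.4 and 2.6 for n = 10, 11, 12 and 13, so at most 2 at every n.

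**Step 2: upper limits.** For 0/n the limit is 1 − a^(1/n), where a is the upper-tail probability. For example, 1 − 0.025^(1/10) = 30.8%. For 2/n the limit is the p that solves P(X ≤ 2 | n, p) = a.

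| n | 0 'worse', two-sided | 0 'worse', one-sided | 2 'worse', two-sided | 2 'worse', one-sided | 0.8^n |
|---|---|---|---|---|---|
| 10 | 30.8% | 25.9% | 55.6% | 50.7% | 10.7% |
| 11 | 28.5% | 23.8% | 51.8% | 47.0% | 8.6% |
| 12 | 26.5% | 22.1% | 48.4% | 43.8% | 6.9% |
| 13 | 24.7% | 20.6% | 45.4% | 41.0% | 5.5% |

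Every limit exceeds 20%. The last column says the same thing another way: with a true rate of exactly 20%, zero 'worse' still occurs more than 5% of the time at every n. With zero 'worse', the exact limit first falls below 20% at n=14 one-sided (19.3%) or n=17 two-sided (19.5%).

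**Step 3: how often the 20% part passes.** P(X ≤ 2) = Σ C(n,x) p^x (1−p)^(n−x) over x = 0, 1, 2. At n=10 and p=0.30 this is 0.028 + 0.121 + 0.233 = 0.383.

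| True 'worse' rate | n=10 | n=13 |
|---|---|---|
| 15% | 82.0% | 69.2% |
| 20% | 67.8% | 50.2% |
| 30% | 38.3% | 20.2% |

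Row A also requires overall results that are the same or better, so these are upper bounds on the chance of passing the full rule.

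**Step 4: other intervals, same unit.** With zero 'worse', an exact one-sided 90% limit falls below 20% from n=11 (18.9%), as does a Wilson one-sided 95% limit (19.7%). A Jeffreys two-sided 95% limit does so at n=12 (18.5%) and n=13 (17.3%). Claiming success on zero 'worse' at n=11 to 13 would carry a true error rate of 8.6% down to 5.5% (0.8^n).

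**Step 5: pooled ratings.** Suppose k questions per subject with within-subject correlation ICC. The effective number of ratings is approximately nk / (1 + (k−1)·ICC). Assume k=5 and zero 'worse', with two-sided 95% limits:

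| ICC | n=10: effective number, limit | n=13: effective number, limit |
|---|---|---|
| 0 | 50.0, 7.1% | 65.0, 5.5% |
| 0.5 | 16.7, 19.9% | 21.7, 15.7% |
| 1 | 10.0, 30.8% | 13.0, 24.7% |

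On this unit the answer depends on k and the ICC, neither of which the visible text gives.

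**The case against.** The plan is candid. It calls the analysis descriptive and the sample one of convenience, and sections 6 and 8.1 explain why eligible amputees are scarce. It nowhere says that 20% is a population margin to be excluded. All of that is fair, and it is a reason not to ask for a larger trial. It does not explain why a descriptive share should carry a pass/fail label under a confirmatory aim.

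Several stronger readings are tempting, and the documents do not support them.

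- A reader might infer that no possible result could exclude 20%. That holds only with the subject as unit and an exact 95% limit. The phrase "overall for all questions" may equally mean pooled ratings, and step 5 shows that zero 'worse' could then give a limit below 20%. Even on the subject unit, the one-sided margin at n=13 is narrow (20.6%), and some other intervals fall below 20%.
- A reader might infer that the plan has no rule for combining answers. The annex holding the row A questions is redacted, and sections 10.1 and 10.2 cite a Table 4 that is not in the visible text. Such a rule could be there.
- A reader might infer that the sponsor will report the pilot as confirmed. No section gives reporting wording. The documents show only that the criterion would be met.
- A reader might infer that a pass generally leaves half of users possibly dissatisfied. That describes the boundary case of 2/10; at 2/13 the two-sided limit is about 45%.

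One uncertainty points the other way. Row A's criterion names only Rheo Knee, while its hypothesis refers to the prescribed prosthesis. If the criterion applies to former Rheo Knee users only, n is smaller and the limits are wider.

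**Conclusion.** The concern holds in conditional form. Table 5 row A accepts 'no worse' on an observed proportion, with no measure of uncertainty and under an aim to confirm. With one overall rating per subject, a pass at the boundary leaves an exact two-sided 95% upper limit of 55.6% (2/10) to 45.4% (2/13), and zero 'worse' leaves 30.8% to 24.7%. An exact 95% limit therefore cannot exclude 20% on that unit. The 20% part alone would pass 38% (n=10) or 20% (n=13) of the time at a true rate of 30%. These figures rest on the subject as unit, which is assumed. If ratings are pooled, the limit cannot be fixed from the visible text, but the missing uncertainty statement and the undefined unit remain.

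**What to change.** In Table 5 row A and section 10.1:

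- State the unit of analysis. If it is the subject, state how a subject's answers combine into one overall rating (for instance, 'worse' on ramps but 'better' on stairs). Report the number and proportion 'worse' with an exact (Clopper-Pearson) two-sided 95% interval beside the 20% benchmark.
- If ratings are pooled over questions, use an interval that allows for clustering by subject.
- State that meeting the benchmark is a descriptive result for this sample and does not by itself establish 'no worse'.
- State whether row A covers all subjects or former Rheo Knee users only, so that the denominator is fixed.

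In section 6, reword 'confirm' to match.

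The cost is one interval, a short pre-specified combination rule and some rewording. No extra subjects, visits or data are needed. The downside for the sponsor is a less favourable stated conclusion.

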Device(s) being tested:	Device under evaluation: Navii (also known as Rheo Knee 4), a pre-market passive exo-prosthetic microprocessor controlled knee device. Comparator: Subjects prescribed passive microprocessor knee, marketed device. For simplification the device under evaluation in this investigation will be referred to as “investigational device” throughout this document.	
Instruments and equipment:	Instruments: 
 • SFCS Socket fit comfort score • PEQ ambulation subscale (Questions 13A, 13B, 13C, 13D, 14E, 14F, 14G, 14H) • PEQ Utility questions (Questions 2G, 2F) • PEQ Satisfaction Questions (Questions 16A, 16B) • Device and performance specific questionnaires • TUG, 2MWT, ABC, PLUS-M. Equipment: 
 • Investigational device (see section 5 Investigational device) • Other components as applicable (prosthetic feet, adapters) • Tools for fitting • Detailed protocol • Case report forms (CRFs); in Smart-Trial – Tablet/computer OR Printed out Case report forms (CRFs including instruments listed above) 	
Subjects recruited:	Inclusion criteria:	Exclusion criteria:
Procedures:	
 - 45Kg < body weight < 136Kg - Cognitive ability to understand all instructions and questionnaires in the study; - Unilateral TF/KD amputees that are regular prosthesis users for at least 3 months - Current MPK users (passive MPKs only) regularly performing descent activities (stairs/ramps) - Age ≥ 18 years - Willing and able to participate in the study and follow the protocol 	
 - Users with stump pain - Users with socket problems - Pregnant Users - Users using Power Knee, Kenevo or mechanical knees as their prescribed prosthesis - Alignment that cannot be matched with the Navii setup, as described in Instructions for use. - Osseointegration

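### Hypothesis B claims a good level of satisfaction, but its acceptance criterion only asks that Navii is not worse than the prescribed knee

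*Combined protocol and SAP*

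**What the plan says.** Section 7, Table 5, row B gives the hypothesis as "Navii shows a good level of overall satisfaction in activities of daily living". No comparator is named. The methods are "Subset of PEQ (see Annex 8.4) Specific Questions (see Annex 8.8"), the endpoint is a PEQ rating, and the whole acceptance criterion reads "Comparison Subset PEQ pre vs post. Navii not worse than prescribed".

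The matching objective, in the synopsis and in Section 7, is that "the overall satisfaction for activities of daily living will be evaluated after a certain time of use (4 weeks home use"). It defines no level either. For all hypotheses, Section 7 sets the baseline mean on the comparator (μ1) against μ2, which "is the average of measurements at 4 week follow up (investigational device"). Section 10.1 assigns B to a mixed model with MPK type as fixed effect and subject as random effect. Sections 10.1 and 10.2 refer to the endpoints table for the acceptance criteria.

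The synopsis lists the PEQ content as three labelled sets: "PEQ ambulation subscale (Questions 13A, 13B, 13C, 13D, 14E, 14F, 14G, 14H"), "PEQ Utility questions (Questions 2G, 2F") and "PEQ Satisfaction Questions (Questions 16A, 16B").

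**The concern.** The hypothesis is about how satisfied users are on Navii. The rule is about whether they are less satisfied than before. These are different questions, and an answer to the second does not settle the first. If the rule is applied as written, a pass on row B would be reported under a hypothesis that speaks of a good level, although nothing in the readable rule refers to a level. The error can also run the other way: users could be well satisfied with Navii and row B could still fail because they were slightly more satisfied with their own knee.

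Satisfaction after home use is the one additional objective the protocol states, and Section 7 links the hypotheses to clinical claims. The wording of row B is therefore likely to carry into the report.

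**Working it through.** The plan gives no power, alpha, margin or calculated sample size for B, so there is no figure to reproduce. The main check is a comparison of texts; the numbers after it are illustrations.

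**1. Rows side by side.** Rows C, D and E each state that Navii is no worse than the prescribed MPK, and each criterion asks for no significant deterioration. Hypothesis and criterion are both relative. Row B alone joins a claim about a level to a comparative rule.

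**2. In symbols.** Let c be the score that counts as good and m ≥ 0 the fall still accepted as not worse. The plan states neither.
- Hypothesis B: μ2 ≥ c.
- Criterion B: μ2 − μ1 ≥ −m.
- If μ1 = μ2 < c, the criterion is met and the hypothesis is false.
- If μ2 ≥ c and μ1 > μ2 + m, the hypothesis is true and the criterion is not met.

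Neither statement implies the other, whatever c and m are.

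**3. Illustration of the first case.** The inputs are assumed, except n = 13 (the maximum in Section 10.2): PEQ on 0-100, baseline SD 15, SD of differences 15, no true difference, good taken as an observed mean of at least 70, 100,000 simulated trials. The follow-up SD is √(15² + 15²) = 21.2 and its standard error 21.2/√13 = 5.88. At a true mean of 60, the chance of an observed mean of 70 or more is therefore 1 − Φ(10/5.88), about 4.5%, and the simulation agrees.

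| Common true mean | Pass, no significant fall (one-sided 0.05) | Pass with Navii mean below 70 | Pass, point estimate ≥ 0 | Pass with Navii mean below 70 |
|---|---|---|---|---|
| 40 | 95% | 95% | 50% | 50% |
| 60 | 95% | 90% | 50% | 46% |
| 80 | 95% | 3% | 50% | 0.1% |

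The pass rate does not move with the level under either reading of not worse.

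**4. The relative rule itself.** Rewording B is not enough if not worse stays undefined. With a paired t-test and no margin, a true fall of 0.5 SD of the differences still gives no significant reduction in 48% of trials at n = 13 and 57% at n = 10 (one-sided 0.05), or 62% and 71% at one-sided 0.025. Ten is the minimum number of completers in Section 8.3.

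The half-width of a 95% CI is t(0.975, n−1)/√n: 0.60 SD at n = 13 and 0.72 SD at n = 10. With no true difference, the chance that the CI excludes a given margin is:

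| Margin (SD of differences) | n = 13 | n = 10 |
|---|---|---|
| 0.5 | 38% | 29% |
| 0.8 | 75% | 62% |
| 1.0 | 91% | 80% |

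**5. Item count.** 8 ambulation + 2 utility + 2 satisfaction = 12 listed items, of which 2 are satisfaction items. This is a count only, because no readable text says how the items are combined for B.

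**The case against.** The best defence is that the benchmark is a sound one. Section 6 describes MPKs as standard of care, Section 8.2 calls passive MPKs widely accepted and beneficial, and users with stump pain or socket problems are excluded. Being no worse than such a device might be a reasonable meaning of good. That would be defensible if the plan said so, but no readable text does, and the standing of the comparators does not turn a difference into a level. It does mean that low scores on both knees are a logical possibility; nothing in the documents shows them to be likely.

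Annexes 8.4 and 8.8, the formulas in Section 7 and the list of claims are not readable, and a cut-off or scoring rule may be there. This limits what can be said about scoring. It leaves the mismatch in place, because the criterion in row B reads as complete and cites no threshold.

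Two stronger readings are tempting. The first is that the trial cannot show a good level at all. The documents do not support that: PEQ is collected on Navii at 4 weeks and the Specific Questions are a named method for row B, so the level can be described even though the pass rule does not test it. The second is that satisfaction is diluted to 2/12 = 17% of the score. That presumes an equally weighted pooled mean. The synopsis lists three separate sets and Section 8.1 speaks of a set of subscales, which fits separate scoring at least as well.

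It is also fair that B is not the primary hypothesis, and that overall satisfaction is absent from the ranked endpoints in Section 8.1.

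**Conclusion.** The point holds as a mismatch between hypothesis and criterion within one table row. A pass on row B would show at most that the PEQ subset was not worse than with the prescribed knee, and even that needs a definition of not worse that the readable text lacks. It would not establish a good level of satisfaction. This conclusion rests on the visible wording of row B, the contrast in Section 7 and the model in Section 10.1. The simulated rates depend on the assumed scale, SDs and cut-off, and serve only to show that the rule is insensitive to level. The effect is confined to the satisfaction claim on a non-primary hypothesis.

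**What to change.** Restate hypothesis B, and any conclusion drawn from it, as: satisfaction in daily living with Navii is no worse than with the prescribed MPK. Report the paired PEQ difference with its 95% CI, and judge it against a margin that the sponsor states and justifies before the data are seen; a CI without a decision rule does not establish no worse. State which items or scales decide B. Show satisfaction items 16A and 16B separately from the ambulation and utility items, and report the 4-week Navii PEQ level and the Specific Questions descriptively.

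If the claim of a good level is kept, prespecify and justify an absolute cut-off for the 4-week Navii score. If the redacted annex already contains one, cite it in row B.

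The rewording needs no new data, visits or subjects. Its cost is a narrower claim. The margin or the cut-off is more work, since the documents offer no basis for a value, and with 10 to 13 subjects only a fairly wide margin could be excluded with good probability.
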